## MEDICAL PROTOCOL (HRP-590)

## PROTOCOL TITLE: VISUAL SURROUND SUPPRESSION UNDER PSILOCYBIN

VERSION DATE: May 18, 2023

|  |                                 |
|--|---------------------------------|
| Prisoners  | Excluded from Participation     |
| Adults lacking capacity to consent and/or adults with diminished capacity to consent, including, but not limited to, those with acute medical conditions, psychiatric disorders, neurologic disorders, developmental disorders, and behavioral disorders | Excluded from Participation     |
| Non-English speakers   | Excluded from Participation     |
| Those unable to read (illiterate)  | Excluded from Participation     |
| Employees of the researcher  | Excluded from Participation     |
| Students of the researcher   | Excluded from Participation     |
| Undervalued or disenfranchised social group  | Excluded from Participation     |
| Active members of the military (service members), DoD personnel (including civilian employees)   | Excluded from Participation     |
| Individual or group that is approached for participation in research during a stressful situation such as emergency room setting, childbirth (labor), etc.   | Excluded from Participation     |
| Individual or group that is disadvantaged in the distribution of social goods and services such as income, housing, or healthcare.   | Included/Allowed to Participate |
| Individual or group with a serious health condition for which there are no satisfactory standard treatments.   | Excluded from Participation     |
| Individual or group with a fear of negative consequences for not participating in the research (e.g. institutionalization, deportation, disclosure of stigmatizing behavior).  | Excluded from Participation     |
| Any other circumstance/dynamic that could increase vulnerability to coercion or exploitation that might influence  | Excluded from Participation     |

|  |  |
|--|--|
| consent to research or decision to continue in research. |  |
|--|--|

Additional Safeguards: Disadvantaged groups will be Included/Allowed to Participate as part of this research but information will not be collected as to the participants status.

Therefore, this research does not add any additional risk to this group. Participant confidentiality will be protected. Participants will have the freedom to decline participation and the right to withdraw at any time without penalty. Participant confidentiality will be protected. Participants will have the freedom to decline participation and the right to withdraw at any time without penalty.

## **10.0 Local Number of Participants**

### *10.1 Local Number of Participants to be Consented:*

Local Number of Participants to be Consented: 46 participants are needed for data analysis and we anticipate needing to consent 75 participants to meet that goal.

## **11.0 Local Recruitment Methods**

### *11.1 Recruitment Process:*

- We will post advertisements in the community via flyers and local newspapers.
- We will advertise through the internet, social media (Facebook, Twitter, Meetup, etc.) and community outlets about our study. We will engage a HIPAA compliant and IRB-approved system connected with a REDCap screening form.
- We will maintain a social media presence to promote the study and enhance visibility to the community.
- We will make regular presentations about the research to community organizations including neighborhood groups and the Psychedelic Society of Minneapolis member base.

### *11.2 Identification of Potential Participants:*

- For physical flyers in the community, potential participants will self-identify based on limited information present. They will contact research staff via phone and/or email.
- For internet and social media advertisements, potential participants will self-identify based on limited information present. They will contact research staff via phone and/or email or REDCap form.

## MEDICAL PROTOCOL (HRP-590)

### PROTOCOL TITLE: VISUAL SURROUND SUPPRESSION UNDER PSILOCYBIN

VERSION DATE: May 18, 2023

- Social media presence will direct traffic to IRB-approved website with contact information for the research team listed and a link to the REDCap screening survey (see Appendix A).
- At community presentations potential participants will not be identified by research staff. Potential participants will have the opportunity to self-identify and request more information about research participation.

#### *11.3 Recruitment Materials:*

- Internet advertisement (for public display, potential participant self-identify)
- REDCap survey (basic eligibility criteria to determine who to follow up with over phone/zoom)
- Phone script (study summary to potential participants during phone screen)
- Phone screen (telephone screening form for potential participant eligibility)

#### *11.4 Payment:*

Participants will be compensated directly using the Greenphire ClinCard. Each task completed will have attached a specific compensation amount. Once the task is completed research staff will load the amount attached to that task on to the participants Greenphire ClinCard. Participant compensation will provide participants \$30/hour for their time on psilocybin or control dosing days (two 8-10 hour sessions, \$600), and \$20/hour for other assessments and study visits (Baseline testing, preparatory sessions, 7 MRIs, 4 follow up visits = 47 hours, \$940). Total possible compensation per participant = \$1540. All participants will complete a W-9.

## **12.0 Withdrawal of Participants**

### *12.1 Withdrawal Circumstances:*

Participants will be withdrawn from the research study if any of the following occur while enrolled: 1) participant meets any exclusionary criteria; 2) participant becomes suicidal with intent and plan; 3) participant engages in other harmful behavior towards themselves or others that requires urgent/emergency medical care; 4) participant experiences intolerable adverse effects from the psilocybin or niacin, including allergic reaction; 5) participant fails to adhere to protocol requirements; and/or 6) participant withdraws consent. Decision to withdraw based on these criteria will be determined at the PI's discretion.

### *12.2 Withdrawal Procedures:*

## MEDICAL PROTOCOL (HRP-590)

### PROTOCOL TITLE: VISUAL SURROUND SUPPRESSION UNDER PSILOCYBIN

VERSION DATE: May 18, 2023

If a participant withdraws or is withdrawn from the research study, no more data will be collected on them. Previous data collected will be stored and analyzed as planned, unless exclusionary criteria is met. If the participant is withdrawn they will be notified by phone or in-person and any scheduled appointments for the research study will be cancelled.

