## MEDICAL PROTOCOL (HRP-590)

### PROTOCOL TITLE: VISUAL SURROUND SUPPRESSION UNDER PSILOCYBIN

VERSION DATE: May 18, 2023

users, although their occurrence is rare and in most cases are very brief, not regarded as detrimental, and sometimes even regarded as pleasurable (Johnson et al., 2008). Hallucinogen persisting perception disorder (HPPD), a condition in which the acute perceptual effects of the drug persist for prolonged periods after the peak effects have subsided, is extremely rare, mostly associated with LSD use in combination with cannabis, and has not been reported as having occurred in participants in any modern studies with psychedelic drugs (Martinotti et al., 2018). Nonetheless, careful follow-up on perceptual abnormalities is recommended (Johnson et al., 2008).

The relative safety of psilocybin extends beyond controlled clinical settings, as epidemiological data on illicit and ritual use shows that adverse reactions leading to hospitalization are relatively rare (Johnson et al., 2018b; Leonard et al., 2018). Since there is little to no risk of physical overdose (Brown et al., 2017; Johnson et al., 2008), most hospitalizations resulting from illicit use in the general population are due to emotional distress and unstable mental states (Leonard et al., 2018) and subside within 48 hours (Johnson et al., 2018b; Tylš et al., 2014).

In summary, psilocybin has a proven track record of safety when administered in controlled experimental settings that follow established protocols (Brown et al., 2017; Dos Santos et al., 2018; Hasler et al., 2004; Johnson et al., 2008; Johnson and Griffiths, 2017). Although not completely without risks, psilocybin does not impose unusual danger compared with other standard experimental treatments and interventions.

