**Visits 3 and 5**

**Digital Journal.** Throughout the study, participants will also be asked to keep a digital journal that will be submitted after each dosing session (**Visit 3 and Visit 5**), and at the end of the study (**Visit 7**) to document their qualitative and subjective experience for content analysis. Within 1 week after their dosing session, participants will be asked to write for 30-60 minutes to describe the content of their experience, and any reflections or interpretations they derived from the experience to help determine the subjective information of their drug experience. These will be collected in a REDCap form (see Appendix F) and sent out to participants via email or text after completion of the dosing session, and a follow-up email or text towards the end of the week if they have not completed the form.

**Debriefing session.** One day following each dosing session (Visits 3a and 5a), study staff will meet with the participant for about 60 minutes (either in person at CMRR prior to MRI, or remotely over Zoom) to discuss the dosing session the previous day, and debrief on anything they want to discuss or process with the study staff.

**Blood Draws.** All blood draws will be performed by the clinical staff onsite, and blood samples will be stored at the Cytokine Reference Lab on campus for cytokine assays, and serum chemistry will be processed by Fairview. Samples will be collected at baseline (**Visit 1**) and again at **Visit 3 (a,b,c)** and **Visit 5 (a,b,c)**.

**MRI.** See CMRR section below (5.5).

All neuropsychiatric, baseline and follow up testing will be conducted in the ARC (or Zoom, if appropriate), and all fMRI sessions will be collected at CMRR. All dosing sessions and EEG data collection will be performed in the CRU. The study coordinator will greet each participant upon arrival, and escort them to the different locations for data collection and testing.

MEDICAL PROTOCOL (HRP-590)

PROTOCOL TITLE: VISUAL SURROUND SUPPRESSION UNDER PSILOCYBIN

VERSION DATE: May 18, 2023

Participants will be monitored at each visit for adverse events (*Zoom option*), including for suicidal thoughts, and given at least 2 weeks between dosing/testing sessions for drug washout. After completion of final dosing sessions, participants will undergo follow up assessments at 2 weeks (**Visit 6**) and 2 months after the final dosing session for study closeout (**Visit 7**).

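### Section 12.2 ends all data collection at withdrawal with no exception for safety withdrawals, so adverse events still open then have no planned outcome data in the trial record

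*Combined protocol and SAP*

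**What the plan says.** Section 12.1 (Withdrawal Circumstances) lists six grounds. Three are direct safety events: "participant becomes suicidal with intent and plan"; "participant engages in other harmful behavior towards themselves or others that requires urgent/emergency medical care"; and "participant experiences intolerable adverse effects from the psilocybin or niacin, including allergic reaction". Newly meeting an exclusion criterion is another. The list closes with "Decision to withdraw based on these criteria will be determined at the PI's discretion".

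Section 12.2 (Withdrawal Procedures) gives the consequence: "If a participant withdraws or is withdrawn from the research study, no more data will be collected on them". For a participant whom the study withdraws, "any scheduled appointments for the research study will be cancelled". Data already collected are kept and analysed, except where an exclusion criterion has been met.

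Section 5.2 (Visits 3 and 5) sets the safety follow-up: "Participants will be monitored at each visit for adverse events", with a Zoom option, and a close-out visit two months after the last dosing session. Section 18.2 requires an adverse event log for the DSMB that shows, among other items, the duration and corrective treatment of each event.

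**The concern.** Section 12.2 treats all withdrawals alike. It does not distinguish a participant who withdraws consent from one whom the PI removes for a safety reason, or stopping study drug and research testing from leaving safety follow-up. Followed as written, it stops safety data because harm has occurred.

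What is at stake is the late safety record. The events most likely to lead to withdrawal would be recorded at onset, with no planned research assessment of how long they lasted or how they ended. Assessments through Visit 7 would come only from people who stayed enrolled. Section 13.1 names prolonged psychotic episodes and lasting perceptual abnormalities as long-range risks. Those are outcomes that only later assessment can confirm or exclude.

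**Working it through.** The plan states no figure on this point, so there is none to reproduce. The check compares sections and counts scheduled assessments.

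1. **Scope of the rule (12.2).** The stop on data applies both to participants who withdraw and to those who are withdrawn. The cancelling of appointments applies to those who are withdrawn. Neither sentence makes an exception for an open adverse event.

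2. **Who falls under it (12.1).** The safety grounds quoted above lead to the same procedure as non-adherence or withdrawal of consent.

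3. **What was scheduled (Schedule of Events, Section 5.2).**
   - Adverse event review: Visits 1 to 7.
   - C-SSRS: Visits 1 to 7.
   - MINI-7: Visits 1 and 7 only, so one post-baseline administration.
   - Timing: Visit 2 at Week 2, Visit 4 at Week 4, Visit 7 at Week 12.

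4. **What is lost.**
   - Withdrawn just after Visit 2: Visits 3, 4, 5, 6 and 7 are lost, which is 5 of 7 scheduled adverse event reviews and C-SSRS. Follow-up lost: 12 − 2 = 10 weeks.
   - Withdrawn just after Visit 4: Visits 5, 6 and 7 are lost, which is 3 of 7. Follow-up lost: 12 − 4 = 8 weeks.
   - In both cases the Visit 7 MINI-7 is lost, leaving none after baseline.
   - The weeks are nominal, because the schedule allows window adjustments of 7 to 14 days.

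5. **What the record needs (18.2).** The DSMB log calls for the duration and corrective treatment of each event. For an event still open at withdrawal, duration cannot be completed if nothing more is collected, and later treatment would also go unrecorded. This is a direct conflict with 12.2.

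6. **Whether another section supplies the outcome.**
   - Section 5.2 (Safety) has the team assess adverse effects and directs people with drug-related psychological effects to a mental health professional.
   - Section 5.2 (assessment before discharge) allows admission for further care.
   - Section 20.1 provides treatment for research injury, with follow-up care as needed.
   - Section 18.2 sends any SAE at once to the DSMB, the FDA and the IRB.

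   These cover care, referral and notification. None says that outcomes are recorded for the trial after withdrawal, and 12.2 says that they are not.

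7. **How many people.** The documents give no rate of withdrawal for adverse events, so the number affected cannot be computed.

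**The case against.** The strongest reply is that participants are not abandoned. Section 12.2 cancels research appointments, not clinical contact, and the care, referral, injury and SAE provisions above are not conditioned on staying enrolled. This stands against a stronger reading that a reader might infer, namely that the worst safety outcomes are never followed to resolution. The documents do not support that. Clinical follow-up may well take place, and the crisis plan, discharge assessment and DSMB charter (Appendices D, E and G) are cited but are not in the text available for review. The reply does not restore outcome data to the trial record.

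Second, withdrawal is discretionary: the PI could keep an affected participant enrolled. That is correct, so a safety event need not trigger 12.2. But the discretion covers only whether to withdraw. Once it is used, 12.2 leaves no room to collect safety data.

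Third, some of the apparent contradictions are weak. The sentence in Section 4.1, "Nonetheless, careful follow-up on perceptual abnormalities is recommended", is a recommendation cited from the literature, not a procedure. Section 5.2 promises adverse event monitoring at visits; it does not promise that everyone attends through two months whatever happens. Both points stand. The firm conflict is with the DSMB log; with Section 5.2 there is tension rather than contradiction.

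Fourth, Section 3 names no safety endpoint, so the primary psychophysical and secondary EEG endpoints are not at issue here. That also stands.

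**Conclusion.** The point holds as a defect in the safety record. Section 12.2 permits no safety data after withdrawal, even when the PI withdraws someone because of harm, and it conflicts with the duration and corrective-treatment items of the DSMB log. For each person affected, the loss is 5 of 7 scheduled adverse event reviews and C-SSRS (about 10 weeks) if withdrawn just after Visit 2, or 3 of 7 (about 8 weeks) if just after Visit 4, plus the only post-baseline MINI-7 in either case. Follow-up not collected in that window cannot be recovered later.

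This rests on reading 12.2 as written, on taking visit timing and MINI-7 administrations from the Schedule of Events, and on the unavailable appendices containing no overriding rule.

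Two further inferences are tempting but unsupported. The first is to turn the drop-out allowance in Section 15.2 into a number of concealed lasting harms. That section gives no reasons for drop-out, and the onset of a triggering event would ordinarily already be logged. The second is to extend the point to early termination of the study. Section 12.3 does not say that follow-up of dosed participants stops; for a safety termination it says that adverse event data will be evaluated.

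**What to change.** Reword 12.2 to separate two things: stopping study interventions and research testing, and leaving safety data collection. Participants whom the PI withdraws under 12.1, and who have not withdrawn consent, would continue the safety assessments already scheduled: adverse event review and C-SSRS at the remaining time points, and the Visit 7 MINI-7. These can be remote where the protocol allows; Section 5.2 already gives a Zoom option for adverse event monitoring and for the psychopathology assessment. Data collection would end only on withdrawal of consent.

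Reconcile the new text with the Safety and Visits 3 and 5 paragraphs of Section 5.2, with the DSMB log in 18.2, and with 20.1, so that it is clear where outcomes after withdrawal are recorded. The change concerns data collection only. It leaves untouched the grounds for withdrawal, the PI's discretion and clinical care.

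The cost is an amendment to the protocol and consent wording, and a few remote contacts for those withdrawn. No new instrument or visit type is needed.

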**Dosing Session.** Dosing sessions will involve 8 hours of preparatory visits (2a-d) before the day of the first dosing session, and one hour before the second dosing session (4a), which will occur either in person in the dosing room in CRU or over Zoom if preferred, and will be recorded for both audio and video. During these 4 preparatory visits, which will last approximately 2 hours each prior to the first dosing session, and 1 hour prior to the second dosing, for a total of 9 hours, participants will meet with at least one of their dosing session monitors that will be sitting with them, and discuss what to expect during the dosing session, and what food preferences they have for two meals they will be offered during their time in the CRU. This visit also serves to help build rapport and common understanding between the two monitors and the participants prior to the dosing session, to review the participants personal history and anything that might come up during the dosing sessions (see visual aid that will be used for this in Appendix H), as well as an opportunity to educate the participants more on the procedures that will occur during the day, and the purpose of the study and the characteristics of the study drug. Participants will be asked to get at least 6-8 hours of sleep, and get dropped off in the morning by a trusted familiar individual. Once checked and settled into the room, participants will be allowed the option to remove their mask during the day, if that feels more comfortable for them. Prior to the administration of psilocybin or placebo, the participants will be given a brief physical exam, including a pregnancy test, breathalyzer for alcohol content, and measuring weight and vital signs. Participants will then be asked to answer a few questions on a checklist about their substance use since being enrolled in the study to assess whether they have engaged in activities that would make them ineligible and withdrawn from the study (see Appendix C). If they pass, we will proceed to the dosing session after a team member from the CRU and one of the study team members will walk over to IDS to receive the study compound, and escort it back to the testing room. The dosing sessions will be recorded using video equipment in the room for the duration of the visit.

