**Assessment of participant before discharge from dosing session.** Prior to being released to a trusted family member or friend at the end of the session, we will assess the participant to make sure they are safe to leave. We will do a physical and mental health assessment, including measuring vital signs, ECG, mental health status and responses to questions about thought processes, such as suicidal ideation with the CSSRS or other concerning symptoms (see appendix E). If the participant is displaying symptoms that need to be continually monitored, we will discuss with the clinical staff whether to admit them for follow-up care. Additional follow-up care that is needed will be billed to the participants health insurance.

MEDICAL PROTOCOL (HRP-590)

PROTOCOL TITLE: VISUAL SURROUND SUPPRESSION UNDER PSILOCYBIN

VERSION DATE: May 18, 2023

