#### 7.2 Sharing of genetic testing: N/A

7.2.1 Disclosure of results: N/A

7.2.2 If returning results to participants: N/A

7.2.3 Future analysis of genotypes: N/A

## 8.0 Study Population

MEDICAL PROTOCOL (HRP-590)

PROTOCOL TITLE: VISUAL SURROUND SUPPRESSION UNDER PSILOCYBIN

VERSION DATE: May 18, 2023

8.1 Inclusion Criteria:

- Gender: Any
- Age: 25-65
- Demographic group: Any
- Have given written informed consent
- Have at least a high-school level of education or equivalent (e.g. GED), and be able to read and write in English
- General health status: Participants should be in good physical and psychiatric health.
- Experience taking psilocybin (at the PI's discretion).
- Participants must also have a person that can reliably transport them to and from the CRU for dosing session days.
- Geographic location: Minnesota counties that are approximately within 1 hour driving distance to Twin Cities, including not limited to Hennepin, Ramsey, Washington, Anoka, Wright, Carver, Scott, Dakota, Sherburn
- Agrees to adhere to current COVID-19 safety precautions implemented at MHealth/Fairview
- Agrees to refrain from using recreational drugs while enrolled in the study, including, but not limited to, hallucinogens, ketamine, and marijuana.

8.2 Exclusion Criteria:

- Current or past history of meeting DSM-5 criteria for schizophrenia spectrum or other psychotic disorders (except due to another medical condition), or Bipolar I or II Disorder, personality disorder, major depressive disorder, posttraumatic stress disorder, panic disorder, obsessive compulsive disorder, dysthymic disorder.
- Current or past history within the last 5 years of meeting DSM-5 criteria for a moderate or severe alcohol or drug use disorder (excluding caffeine, nicotine, and hallucinogens)
- Those with a first or second-degree relative with a current or past history of meeting DSM-5 criteria for schizophrenia or other psychotic disorders or bipolar I or II disorder, because they might have an underlying genetic susceptibility for psychosis.
- Presence of symptoms of the following DSM-5 disorders within the past 6 months (as assessed by the MINI-7):
  - Major depressive Episode
  - Suicidality
  - Manic and Hypomanic Episodes
  - Panic disorder
  - Agoraphobia
  - Social Anxiety Disorder
  - Obsessive-Compulsive Disorder
  - Posttraumatic Stress Disorder
  - Alcohol Use Disorder
  - Substance Use Disorder (Non-Alcoholic)
  - Psychotic Disorders and Mood Disorders with Psychotic Features

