## MEDICAL PROTOCOL (HRP-590)

### PROTOCOL TITLE: VISUAL SURROUND SUPPRESSION UNDER PSILOCYBIN

VERSION DATE: May 18, 2023

disorder, or double vision, or tattoos that were done less than 4 weeks from the first scheduled MRI.

- Significant movement disorders including tardive dyskinesia that could disrupt EEG recordings will also be excluded.
- Uncontrolled hypertension, with an average blood pressure reading across 4 measurements over 2 separate days greater than 140/90mmHg.
- ECG with a QTc greater than 450 msec, based on the [FDA Guidance of Clinical Evaluation of QT/QTc Interval Prolongation and Proarrhythmic Potential for Non-Antiarrhythmic Drugs](#).
- Unwilling to adhere to current COVID-19 safety precautions.

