## MEDICAL PROTOCOL (HRP-590)

PROTOCOL TITLE: VISUAL SURROUND SUPPRESSION UNDER PSILOCYBIN

VERSION DATE: May 18, 2023

visit/procedure. Consent will be documented in writing by signature on the Consent Form and completed MacCAT-CR form. Research staff obtaining consent will also sign each of these applicable forms.

Additionally during the consent process, participants will be instructed on criteria that would disqualify them during the course of the study, including 1) participant meeting any exclusionary criteria during the course of the study; 2) participant becomes suicidal with intent and plan; 3) participant engages in other harmful behavior towards themselves or others that requires urgent/emergency medical care; 4) participant experiences intolerable adverse effects from the psilocybin or niacin, including allergic reaction; 5) participant fails to adhere to protocol requirements; and/or 6) participant withdraws consent. Decision to withdraw based on these criteria will be determined at the PI's discretion.

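### Section 12.2's exception for exclusion criteria has no time limit, so it permits a dosed participant's data to be left out because a criterion was first met after dosing (minor)

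*Combined protocol and SAP*

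**What the plan says.** Section 12.2 stops data collection at withdrawal and then sets the rule for data already in hand: "Previous data collected will be stored and analyzed as planned, unless exclusionary criteria is met". It attaches no time point to the exception.

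Section 12.1 opens its list of six grounds with "Participants will be withdrawn from the research study if any of the following occur while enrolled: 1) participant meets any exclusionary criteria" and ends it with "Decision to withdraw based on these criteria will be determined at the PI's discretion". Section 21.1 repeats the first ground to participants as "participant meeting any exclusionary criteria during the course of the study". The other five grounds are suicidality with intent and plan, harmful behaviour, intolerable adverse effects, non-adherence and withdrawal of consent.

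Some exclusion criteria in section 8.2 can be met, or are measured again, after a dose:

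- **QTc.** The criterion is "ECG with a QTc greater than 450 msec". Before discharge from each dosing session, section 5.2 states "We will do a physical and mental health assessment, including measuring vital signs, ECG, mental health status", and the Schedule of Events lists ECG at Visits 1, 2 and 4.
- **Psychiatric symptoms.** The criterion begins "Presence of symptoms of the following DSM-5 disorders within the past 6 months (as assessed by the MINI-7". The Schedule of Events lists the MINI-7 at Visits 1 and 7 and the C-SSRS at every visit.

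Before each dosing session, so also at Visit 4 after the first dose, a substance-use checklist is used to "assess whether they have engaged in activities that would make them ineligible and withdrawn from the study".

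Section 15.1 compares the C-SSRS, vital signs and diagnostic tests between groups. Section 15.3 plans repeated measures ANOVA and a random-intercept mixed model. Neither defines an analysis population or a missing-data rule.

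**The concern.** Leaving out someone who was ineligible at entry, on information that predates treatment, does not select on a treatment effect. Leaving out someone because of something first observed after a dose can, since the drug may have caused that event. Section 12.2 does not separate the two cases.

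Two kinds of result are exposed. In the between-group comparisons of the C-SSRS and vital signs, a participant could leave the comparison because of the very finding it is meant to show. In the efficacy analysis, someone withdrawn between sessions has baseline and first-session data that the mixed model can use; someone withdrawn after the second session has the complete acute data.

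The research team is blinded to group and order (section 4.2), so the decision is nominally blind. That does not prevent selection when the trigger is itself a post-dose event.

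**Working it through.** **Reading the text.** Section 5.1 places randomisation after all eligibility criteria are confirmed, so a criterion met later is normally a post-randomisation event. Sections 12.1 and 21.1 apply the criteria during enrolment, not only at entry. Section 12.2 exempts those who meet a criterion from being analysed as planned. Section 15 does not override this. Following the text can therefore remove post-dose data because of a post-dose event.

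**The plan's own figure.** Section 15.2 states 92% power with 16 subjects. The effect size and SD are not given, so this cannot be reproduced, only solved backwards. Assuming a paired two-sided 5% test (noncentral t, 15 df), 92% power at n = 16 implies a standardised paired effect of 0.901. At that effect, power is 99.98% with 40 analysed, 99.85% with 32, 92% with 16 and 88% with 14. Power is not the issue.

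**Efficacy shift when both sessions have been completed.** The inputs are assumptions: a proportion p is removed, namely those highest on a post-dose trait that correlates r with the individual response. The shift in the mean of those retained, in SD units, has size r × φ(z) / (1 − p), where z is the upper-p normal quantile.

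| p | φ(z)/(1 − p) | r = 0.3 | r = 0.5 |
|---|---|---|---|
| 0.025 | 0.0584/0.975 = 0.060 | 0.018 | 0.030 |
| 0.05 | 0.1031/0.95 = 0.109 | 0.033 | 0.054 |
| 0.10 | 0.1755/0.90 = 0.195 | 0.059 | 0.097 |

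With r = 0 the shift is zero. Relative to 0.901, the range is 0.018/0.901 = 2.0% to 0.097/0.901 = 10.8%. The standard error of a paired mean with 40 participants is 1/√40 = 0.158 SD, so the largest entry is about 0.6 of one standard error. Removing the stronger responders makes the effect look smaller.

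**Type I error.** In a simulation of 40 paired differences with no true effect, removing the 2 highest (r = 0.3) or the 4 highest (r = 0.5) raised two-sided type I error from 0.05 to about 0.06 and 0.09.

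**Efficacy shift when withdrawal falls between sessions.** Simulation with 20 per sequence; baseline, niacin and psilocybin measures; random-intercept model with a sequence covariate; within-person correlation 0.6 (assumed); k psilocybin-first participants lose the second session. Shifts are against full data, in SDs of the within-person difference, for r = 0.3 / 0.5:

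| k of 20 | Earlier data left out: psilocybin − baseline | Earlier data left out: psilocybin − niacin |
|---|---|---|
| 1 | −0.014 / −0.023 | −0.007 / −0.011 |
| 2 | −0.025 / −0.043 | −0.014 / −0.022 |
| 4 | −0.045 / −0.073 | −0.021 / −0.038 |

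When the earlier data are kept, the shift is about 0.002 or less in absolute value. The planned mixed model therefore already handles these participants if 12.2 lets it.

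**The case against.** **Intended meaning.** The clause may have been meant only for people later found to have been ineligible at entry. That is plausible, and 12.2 does not say outright that data are discarded. But the text does not state that limit, and the time frames in 12.1 and 21.1 point the other way.

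**Scope.** A reader might infer that the most clearly drug-related withdrawals lose their data. The documents do not support this. Participants withdrawn only for suicidality with intent and plan, harmful behaviour, intolerable adverse effects or non-adherence fall outside the exception, and their data are analysed.

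**The checklist.** It is tempting to treat a breach found at Visit 4 as the firm example. Refraining from recreational drugs is an inclusion criterion in 8.1, so a breach may equally be non-adherence, for which data are kept. Which applies is unclear.

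**Psychiatric symptoms.** The criterion is tied to the MINI-7, which the Schedule of Events does not list between doses. The general sentence under Visit 1 in section 5.2, which repeats procedures at later visits, is looser. No text says that a C-SSRS finding counts. The example holds only if a post-dose assessment is taken to meet the criterion.

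**QTc.** Section 5.2 states exclusion on QTc only at Visit 1, so this example rests on the time frame in 12.1. Section 15.1 does not name ECG as a compared outcome, and no link between QTc and surround suppression is given; removal unrelated to response gives no shift.

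**Safety.** A reader might infer that a safety signal could vanish. Section 15 plans no analysis of event proportions, and reporting to the DSMB, FDA and IRB under 18.2 does not depend on 12.2. What remains exposed is the loosely specified comparison of the C-SSRS and vital signs.

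**ANOVA.** In its usual complete-case form, the repeated measures ANOVA drops anyone without Visit 4 whatever 12.2 says. This stands; for withdrawals between sessions the gain is in the mixed model.

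**Conclusion.** The concern holds as a gap in the data rule. The wording permits, but does not require, leaving out data from dosed participants because a criterion was first met after dosing, and no analysis set closes that route. It does not show that this will occur or how often.

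The size is small: about 0.02 to 0.10 SD on the efficacy estimate, under assumed removal of 2.5% to 10% and assumed correlation of 0.3 to 0.5. Some criteria, such as pregnancy, need not be related to response, and removal for them would then cause no bias. The between-session figures also rest on the assumed k and within-person correlation. Neither power nor safety oversight is at risk. Severity: minor.

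**What to change.** 1. **Section 12.2.** Limit the exception to ineligibility that existed before the first dose, judged on pre-dose information and blind to condition and outcome. Otherwise analyse the data collected before withdrawal. State whether a checklist breach counts as an exclusion criterion or as non-adherence for this purpose.
2. **Section 16.1.** It says that all copies of a participant's records are destroyed when consent is withdrawn, whereas 12.2 keeps and analyses earlier data. Reconcile the two.
3. **Section 15.** Analyse efficacy in all randomised participants with available data, using the mixed model already planned. Analyse the C-SSRS, vital signs and other safety measures in everyone dosed, by condition received.
4. **Sensitivity analysis.** Repeat the main analysis without participants who met an exclusion criterion after the first dose. To support this, record for each such case the criterion, the date, and whether it was first met before or after the first dose.

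The cost is short edits to 12.2 and 16.1, an analysis-set paragraph in section 15 and a small addition to the withdrawal record. Sample size, visits and procedures do not change, nor do the rules on who is withdrawn and when. The downside is that a few participants who became ineligible stay in the main analysis; the sensitivity analysis shows whether they matter.
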